1. BACKGROUND AND DESIGN

1.1 Background

Patients with acute respiratory failure (ARF) experience an increased risk of respiratory tract secretion retention due to altered secretion rheology and impaired mucociliary clearance. The use of carbocisteine and hypertonic saline are now being evaluated in patients with ARF as part of the MARCH clinical trial and in this study we will investigate the mechanistic effects of these two mucoactive agents.

1.2 Hypothesis

Treatment of critically ill patients with ARF with carbocisteine, hypertonic saline, or both, will lead to increased mucus hydration and changes in sputum viscosity and elasticity.

1.3 **Aim**

To determine if critically ill patients with ARF treated with carbocisteine, hypertonic saline, or both, experience increased hydration of airway mucus (reflected as a reduced percentage mucus solid content¹).

1.4 Objectives

Primary objective

To measure percentage mucus solid content (dry-to-wet weight ratio) of sputum at Day 0 and Day 3 in critically ill patients with ARF following commencement of treatment with carbocisteine, hypertonic saline, or both, or usual airway clearance management alone.

Secondary objectives

- 1. Measurement of percentage mucus solid content (dry to weight ratio) at Day 0 and Day 7 following commencement of treatment with carbocisteine, hypertonic saline, or both, or usual airway clearance management alone
- 2. Measurement of yield stress (T_c) (derived from sputum viscosity (G') and elasticity (G'')) at Day 0 and Day 3 following commencement of treatment with carbocisteine, hypertonic saline, or both, or usual airway clearance management alone
- 3. Measurement of sputum levels of IL-6, IL-8 and 8-isoprostane at Day 0 and Day 3 following commencement of treatment with carbocisteine, hypertonic saline, or both or usual airway clearance management alone (no mucoactive)
- 4. Measurement of yield stress (T_c) (derived from sputum viscosity (G') and elasticity (G'')) at Day 0 and Day 7 following commencement of treatment with carbocisteine, hypertonic saline, or both, or usual airway clearance management alone
- 5. Measurement of sputum levels of IL-6, IL-8 and 8-isoprostane at Day 0 and Day 7 following commencement of treatment with carbocisteine, hypertonic saline, or both or usual airway clearance management alone (no mucoactive)

Full details of the background to the trial and its design are presented in the protocol.

Doc No: ST06-RD01 Page **5** of **29**

2. OUTCOME MEASURES

2.1 Primary outcome measure

The primary outcome is to measure percentage mucus solid content (dry-to-wet weight ratio) of sputum at Day 0 and Day 3 following commencement of treatment with carbocisteine and/or hypertonic saline.

2.2 Secondary outcome measures

The secondary outcome measure post commencement of treatment will be to measure:

- 1. Percentage mucus solid content (dry-to-wet weight ratio) of sputum at Day 7 following commencement of treatment with hypertonic saline and/or carbocisteine
- 2. Sputum elasticity (G') and viscosity (G") (and yield stress, T_c) at Day 3
- 3. Sputum IL-6, IL-8 and 8-isoprostane levels at Day 3
- 4. Sputum elasticity (G') and viscosity (G") (and yield stress, T_c) at Day 7
- 5. Sputum IL-6, IL-8 and 8-isoprostane levels at Day 7

Doc No: ST06-RD01 Page **6** of **29**

3. DATA

3.1 CRF Forms and variables

Full details of the data to be collected and the timing of data collection are described in the trial protocol.

3.2 Management of datasets

Laboratory data will be collated using MS Excel and transferred via email directly to the NICTU Trial Statistician. The data will be stored in the eTMF (Electronic Trial Master File).

3.3 Data completion schedule

Sputum (endotracheal secretions) samples will be collected at 3 time-points during the study; Day 0 (baseline - at randomisation), Day 3 and Day 7.

3.4 Data verification

Study specific data validation checks will be implemented. The process of data validation ensuring the accuracy and quality of the data will be carried out prior to transfer to NICTU. This will involve an independent cross-check of the data sheet against the raw data, discrepancies that be resolved will be amended, if a discrepancy is unable to be resolved it will be removed from the data sheet and reason for absence will be documented.

3.5 Data coding

The data received will be continuous and therefore data coding is not applicable. The units of each variable will be noted beside the variable name in the received data tables.

Data from the main clinical trial database (MACRO) may also be used throughout the analysis for this EME sub study. Please refer to the MARCH Statistical Analysis Plan for further detail.

Doc No: ST06-RD01 Page **7** of **29**

4. **DEFINITION OF TERMS**

Term	Definition
Per protocol population	Per protocol analysis will be undertaken on the population who receive the complete treatment dose.
	Patients randomised to receive usual airway clearance management (UACM) will be excluded from the per protocol analysis if they commence a non-trial mucoactive.
Compliance	Patients who receive ≥90% available doses will be considered as compliant.
Yield Stress	Measure of the amount of stress applied by the rheometer at which the elastic (G') and viscous (G") moduli cross. The amount of force needed to start a flow or break a solid.

Doc No: ST06-RD01 Page **8** of **29**

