7. ANALYSIS PRINCIPLES

The primary analysis will be conducted on outcome data from the per-protocol population. Analyses will be two-sided and tested at an *a priori* significance level of p=0.05.

We will describe baseline characteristics and follow-up measurements using suitable measures of central tendencies; means and medians with the associated standard deviations/95% confidence intervals (CI) and interquartile ranges for continuous data; and frequencies and proportions for categorical data (including binary data).

Primary outcome

To measure percentage mucus solid content (dry-to-wet weight ratio) of sputum at Day 0 and Day 3 following commencement of treatment with carbocisteine and/or hypertonic saline.

Analysis

Percent solids (wt%) of sputum will be assessed by measurement of pre- and post-desiccation weights of sputum aliquots. Higher percentage weight indicates greater mucus solid content and is associated with disease² and lower percentage mucus solid content i.e. more hydrated indicates lower solid content which is associated with a more normal phenotype.

We will assess the sputum percent solids in all 4 patient cohorts on the MARCH trial at day 3 and compare to sample measurements at baseline (before commencement of treatment).

Comparisons will be made between the groups. Analysis of Covariance (ANCOVA) (and post-hoc tests if significant differences are identified), or non-parametric equivalents, will be used to detect difference in means adjusting for baseline values.

Secondary outcomes

The secondary outcome measure post commencement of treatment will be to measure:

- 1. Percentage mucus solid content (dry-to-wet weight ratio) of sputum at Day 7 following commencement of treatment with hypertonic saline and/or carbocisteine
- 2. Sputum elasticity (G') and viscosity (G") (and yield stress, T_c) at Day 3
- 3. Sputum IL-6, IL-8 and 8-isoprostane levels at Day 3
- 4. Sputum elasticity (G') and viscosity (G") (and yield stress, T_c) at Day 7
- 5. Sputum IL-6, IL-8 and 8-isoprostane levels at Day 7

Analysis

Percent solids (wt%) of sputum will be assessed at day 7, as for the primary objective analysis, and compared to sample measurements at baseline (before commencement of treatment).

Comparisons will be made between the groups using ANCOVA (and post-hoc tests if significant differences are identified) will be used to detect difference in means adjusting for baseline values.

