8.4 Trial treatment

- Number of days on treatment, mean(sd) by treatment arm
- Number of doses, mean(sd) by treatment arm
- Treatment compliance, n(%) by treatment arm
- Reasons for termination of study drug, n(%) by treatment arm
- Did not receive allocated treatment, n(%) by treatment arm
- Received treatment of other group, n(%) by treatment arm
- Antibiotic Usage
 - O Number of patients prescribed antibiotics at least once, n(%) by treatment arm
 - Number of days on antibiotics, mean(sd) by treatment arm
 - o Overall dose (antibiotics), mean (sd) by treatment arm
- **Usual Airway Clearance Management**
 - Number of sessions, mean(sd) by treatment arm
- Non-trial mucoactive administration
 - No. patients with non-trial mucoactive administered, n(%) by treatment arm
 - O Name of mucoactive, n(%) by treatment arm
 - o Total number of days on non-trial mucoactive, mean(sd) by treatment arm
- Consent to Continue/Withdrawal of Consent, n(%) by treatment arm
- Protocol Deviations, no. events (%) by treatment arm, no. patients (%) by treatment arm

Will also be presented by comparison

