8.5 Trial outcomes

Primary Outcome:

Change from day 0 to day 3 in percentage mucus solid content (wt%), mean(SD) by treatment arm, difference in mean with 95% CI.

Comparisons will be made between the groups using ANCOVA (and post-hoc tests if significant differences are identified) will be used to detect difference in means adjusting for baseline values (Day O percentage mucus solid content (wt%)).

Doc No: ST06-RD01 Page 15 of 29

Secondary outcomes:

- Change from day 0 to day 7 in percentage mucus solid content (wt%), mean(SD) by treatment arm, difference in mean with 95% CI.
- Change from day 0 to day 3 in Sputum elasticity (G'), mean(SD) by treatment arm, difference in mean with 95% CI.
- Change from day 0 to day 3 in Sputum viscosity (G"), mean(SD) by treatment arm, difference in mean with 95% CI.
- Change from day 0 to day 3 in yield stress (T_c), mean(SD) by treatment arm, difference in mean with 95% CI.
- Change from day 0 to day 7 in Sputum elasticity (G'), mean(SD) by treatment arm, difference in mean with 95% CI.
- Change from day 0 to day 7 in Sputum viscosity (G"), mean(SD) by treatment arm, difference in mean with 95% CI.
- Change from day 0 to day 7 in yield stress (T_c), mean(SD) by treatment arm, difference in mean with 95% CI.
- Change from day 0 to day 3 in Sputum IL-6, mean(SD) by treatment arm, difference in mean with 95% CI.
- Change from day 0 to day 3 in Sputum IL-8, mean(SD) by treatment arm, difference in mean with 95% CI.
- Change from day 0 to day 3 in Sputum 8-isoprostane, mean(SD) by treatment arm, difference in mean with 95% CI.
- Change from day 0 to day 7 in Sputum IL-6, mean(SD) by treatment arm, difference in mean with 95% CI.
- Change from day 0 to day 7 in Sputum IL-8, mean(SD) by treatment arm, difference in mean with 95% CI.
- Change from day 0 to day 7 in Sputum 8-isoprostane, mean(SD) by treatment arm, difference in mean with 95% CI.

Comparisons will be made between the groups using ANCOVA (and post-hoc tests if significant differences are identified) will be used to detect difference in means adjusting for baseline values.

Will also be presented by comparison

Doc No: ST06-RD01 Page **16** of **29**

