	·	HTS	Carbocisteine	HTS plus Carbocisteine	UACM
		n=	n=	n=	n=
No. of days on treatment*		xx.x(xx.x)	xx.x(xx.x)	xx.x(xx.x)	xx.x(xx.x)
No. of doses		xx.x(xx.x)	xx.x(xx.x)	xx.x(xx.x)	xx.x(xx.x)
	Compliant	n(%)	n(%)	n(%)	n(%)
Treatment Compliance	Not Compliant	n(%)	n(%)	n(%)	n(%)
	Compliance Rate (%)	xx.x(xx.x)	xx.x(xx.x)	xx.x(xx.x)	xx.x(xx.x)
Did not receive allocated tre	atment	n(%)	n(%)	n(%)	n(%)
Received treatment of other	group	n(%)	n(%)	n(%)	n(%)
	28 days elapsed since randomisation	n(%)	n(%)	n(%)	n(%)
	First successful unassisted breathing (maintained for 48 hours)	n(%)	n(%)	n(%)	n(%)
	Study mucoactive related serious adverse event	n(%)	n(%)	n(%)	n(%)
	Discharge from ICU	n(%)	n(%)	n(%)	n(%)
Reasons for termination of	Death	n(%)	n(%)	n(%)	n(%)
study drug	Discontinuation of active medical treatment	n(%)	n(%)	n(%)	n(%)
	Request from Legal Representative or Patient to withdraw from the trial	n(%)	n(%)	n(%)	n(%)
	Decision from the attending ICU physician that the study drug should be discontinued on safety grounds	n(%)	n(%)	n(%)	n(%)
	Other Reason**	n(%)	n(%)	n(%)	n(%)
	Number of patients with non-trial mucoactives administered at least once	n(%)	n(%)	n(%)	n(%)
	Carbocisteine	n(%)	n(%)	n(%)	n(%)
New trial Barragetine	Hypertonic Saline	n(%)	n(%)	n(%)	n(%)
Non-trial Mucoactive Administration	Heparin (non-anticoagulation purposes)	n(%)	n(%)	n(%)	n(%)
Auministration	N-acetylcysteine	n(%)	n(%)	n(%)	n(%)
	Dornase Alfa	n(%)	n(%)	n(%)	n(%)
	Other**	n(%)	n(%)	n(%)	n(%)
	Number of days on non-trial mucoactive	xx.x(xx.x)	xx.x(xx.x)	xx.x(xx.x)	xx.x(xx.x)
Antibiotic Usage	Number of patients prescribed antibiotics at least once	n(%)	n(%)	n(%)	n(%)

Doc No: ST06-RD01 Page **26** of **29**

MARCH EME Statistical Analysis Plan Final 2.0 26/11/2025

		HTS	Carbocisteine	HTS plus Carbocisteine	UACM
		n=	n=	n=	n=
	Number of days on antibiotic	xx.x(xx.x)	xx.x(xx.x)	xx.x(xx.x)	xx.x(xx.x)
	Overall dose	xx.x(xx.x)	xx.x(xx.x)	xx.x(xx.x)	xx.x(xx.x)
Usual Airway Clearance Management	Number of sessions	xx.x(xx.x)	xx.x(xx.x)	xx.x(xx.x)	xx.x(xx.x)
	Mucoactive administration if ongoing	n(%)	n(%)	n(%)	n(%)
	Ongoing data collection during hospital admission	n(%)	n(%)	n(%)	n(%)
Doct vandomisation	On-going data collection following hospital discharge	n(%)	n(%)	n(%)	n(%)
Post-randomisation withdrawal	Confirmation of vital status	n(%)	n(%)	n(%)	n(%)
witiiuiawai	Use of samples collected to date	n(%)	n(%)	n(%)	n(%)
	Use of data collected to date	n(%)	n(%)	n(%)	n(%)
	Other**	n(%)	n(%)	n(%)	n(%)

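### The per-protocol set that carries the primary analysis has no assessment window, so read literally it lets events after the Day 3 sample remove Day 3 results

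*SAP*

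**What the plan says.** Section 7 fixes the primary population: "The primary analysis will be conducted on outcome data from the per-protocol population". No other analysis population is defined, so the entry in Section 4 decides whose Day 3 result counts.

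That entry contains two rules. The dose rule is "Per protocol analysis will be undertaken on the population who receive the complete treatment dose". The second rule concerns patients randomised to UACM, who "will be excluded from the per protocol analysis if they commence a non-trial mucoactive". Neither rule has a start, an end or a link to a sample.

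The next row of the same table defines a separate term: "Patients who receive ≥90% available doses will be considered as compliant". Section 8.4 uses that term as a summary line, "Treatment compliance, n(%) by treatment arm", and the Appendix 1 treatment table reports it in the same descriptive way.

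Section 3.3 places the samples at "Day 0 (baseline - at randomisation), Day 3 and Day 7". Section 8.5 gives the primary outcome as "Change from day 0 to day 3 in percentage mucus solid content (wt%), mean(SD) by treatment arm, difference in mean with 95% CI". The Appendix 1 table of treatment after trial entry lists "28 days elapsed since randomisation" among the reasons for terminating study drug, along with successful unassisted breathing, ICU discharge and death.

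**The concern.** An adherence rule for a Day 3 measurement should look only at what happened up to Day 3. The SAP's rules are not limited in that way, and treatment can apparently run well beyond both sampling days. A patient fully dosed to Day 3 who misses a dose on Day 12 could leave the Day 3 analysis. So could a UACM patient who starts a mucoactive on Day 10.

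Two things are at stake. Valid primary-outcome data would be lost for reasons unrelated to the measurement. Membership could also depend on length of treatment, recovery or later deterioration, all of which follow randomisation and may differ by arm. The stated rules differ by arm as well: UACM patients have no trial doses to miss, and the mucoactive exclusion is written for UACM only. Finally, the trial is open label (Section 6.2), so the primary set should not be left to interpretation at the time of analysis.

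**Working it through.** **1. The plan's own figure.** Section 5 gives a difference of 1.15, SD 2.3, two-sided alpha 0.05 and 90% power. The normal approximation gives n = 2 × (1.960 + 1.282)² / (1.15/2.3)² = 84.1, rounded up to 85 per group. The two-group t-test has power 0.8999 at 85. Allowing for 5% dropout, 85/0.95 = 89.5, so 90 per arm and 360 in total. The sample size reproduces. Its only allowance is for dropout, and the top-up rule counts matched Day 0 and Day 3 samples, not per-protocol members.

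**2. Timing, side by side.**
- Primary outcome: ends at the Day 3 sample (Sections 3.3 and 8.5).
- Dose rule: no period given. If complete means the whole course, doses due after Day 3 count.
- UACM rule: no period given. Taken at its word, starting a mucoactive at any time excludes the patient.
- Longest course: 28 days, inferred from the termination-reason row in Appendix 1.

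An event after the Day 3 sample cannot change that sample, yet nothing in Section 4 stops it from deciding membership. The same holds for Day 7 outcomes and events after Day 7. It is also unclear what complete means for a patient whose drug ends early for one of the listed reasons.

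**3. How much the window could matter (illustration only).** The SAP gives no dose counts or adherence rates. Assume that each dose is received with probability 0.98, independently, at 1 to 4 doses a day. For k doses, the share receiving all of them is 0.98^k. The share receiving at least 90% is the binomial probability of at least 0.9k doses, rounded up.

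| Window | Doses k | All doses | At least 90% |
|---|---|---|---|
| 3 days | 3 to 12 | 0.785 to 0.941 | 0.834 to 0.977 |
| 7 days | 7 to 28 | 0.568 to 0.868 | 0.868 to 0.992 |
| 28 days | 28 to 112 | 0.104 to 0.568 | 0.982 to 1.000 |

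Up to nine doses, one missed dose already falls below 90% (8/9 = 88.9%), so the two criteria coincide. At 12 doses they part (11/12 = 91.7%). Over a full course they select very different sets. The window therefore matters more than the threshold for a Day 3 outcome.

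**4. What a smaller set would cost in power.** This uses the Section 5 t-test inputs, with the share of 85 retained assumed.
- Both groups reduced: 95% kept gives 0.885, 90% gives 0.867, 80% gives 0.825 and 50% gives 0.625.
- One active arm reduced, UACM intact: 80% kept gives 0.863 and 50% gives 0.752.

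**The case against.** A reader might infer that the SAP sets two conflicting thresholds for membership. It does not. Membership has one stated dose criterion. The 90% figure defines compliance, which the SAP never ties to membership, and a looser descriptive measure can sit beside a stricter analysis set. What remains is that the relation between two adjacent adherence terms is unexplained.

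A reader might also infer that the SAP prescribes filtering Day 3 results on later events. For the dose rule, that turns silence into a rule: complete could mean all doses due by the sample, and nothing excludes that reading. The 28 days comes from a table row, not from a stated duration, and the same list shows that many courses may be much shorter. The protocol and the main MARCH SAP are not at hand. This objection limits the point to what the wording allows. It is weaker against the UACM rule, which as worded excludes anyone who starts a non-trial mucoactive, whenever that happens.

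The retention shares are also open to challenge. Missed doses are likely to cluster within patients. At the same average miss rate, clustering leaves more patients with complete dosing than the independence model suggests. The shares cannot apply to UACM either, which has no trial doses. They are therefore not offered as an estimate of the loss.

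**Conclusion.** The point holds in this form: the primary analysis set rests on two rules with no assessment window, and applied literally they can remove Day 3 results because of events after Day 3. This is more than missing detail, because the rule as worded can give a worse analysis than one limited to the period before the sample. It can discard valid data and introduce selection on post-randomisation events. Neither the direction nor the size of any bias can be derived from the SAP.

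The conclusion rests on the inference that treatment can continue past Day 3, which the Appendix 1 row supports. For the dose rule, it also rests on reading complete as the full course, which the text permits but does not state. The retention and power figures show only that the choice of window can be material under assumed inputs; the Section 5 sample size itself is correct. The separate defect, that the dose rule is not related to the compliance definition, is one of clarity and not a contradiction.

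**What to change.** In Section 4, define per-protocol membership separately for each outcome day. For Day 3 outcomes, count only doses due, and non-trial mucoactives started, between randomisation and the Day 3 sample. For Day 7 outcomes, do the same up to the Day 7 sample. State how doses are counted when study drug ends before the sample.

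Reconcile the per-protocol row with the compliance row so that one stated adherence criterion decides membership. If compliance is to remain purely descriptive, say so.

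The cost is a few sentences of SAP wording, plus dated dosing and mucoactive records. Section 3.5 allows use of main trial data, but Section 8.4 lists only totals of days and doses, so confirm that dated records are available before the wording is fixed.

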5. SAMPLE SIZE CALCULATIONS

We plan to analyse sputum samples (at Day 0 and Day 3) collected from 340 patients enrolled in the MARCH trial from across participating ICUs. All consecutive patients recruited to MARCH will be approached to participate in the current study. The main MARCH clinical trial is recruiting a target of 1956 patients across the four arms of the study. Therefore, the proposed sample size for this study should be easily achieved given the anticipated recruitment for the MARCH study.

The sample size has been determined with statistical input from the Northern Ireland Clinical Trials Unit to generate significant differences in the primary outcome of percentage mucus solids in sputum samples of MARCH patients. A sample size of 85 in each of our treatment groups will have 90% power to detect a difference in means of 1.15% assuming that the common standard deviation is 2.3% using a two-group t-test with a 0.05 two-sided significance level. This is equivalent to an effect size of 0.5. Assuming approximately 5% dropout we will collect sputum samples from 360 patients recruited to MARCH trial (90 per arm). If the level of dropout is greater than anticipated, we will continue to collect sputum samples (matched Day 0 and Day 3) towards a target of 340 patients. Although there are no examples of mucus solids measurements in patients with ARF, the sample size generated above is based on mucus solid measurements evaluated in patients with cystic fibrosis and chronic obstructive pulmonary disease¹, the closest disease examples to ARF we could find in the literature.

Importantly, there are likely to be missing samples on day 7 due to extubation, discharge, or death. However, we intend analysing these samples as they will still provide important mechanistic information regarding the effect of both drugs on this day.

Doc No: ST06-RD01 Page **9** of **29**

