Sputum will also be characterized by its elastic (G') and viscous (G'') moduli in order to determine the yield stress value, T_c , a marker of sputum motion. A high T_c , indicates a greater amount of obstruction in the sample and a lower T_c , indicates a decreased amount of obstruction in the sample.

We will assess the sputum elasticity, viscosity and yield stress in sputum samples obtained from all 4 patient cohorts on the MARCH trial at Day 3 and day 7 and compare to sample measurements at baseline (before commencement of treatment).

Doc No: ST06-RD01 Page **11** of **29**

We will also measure sputum levels of IL-6, IL-8 and 8-isoprostane in sputum samples from all 4 patient cohorts on the MARCH trial at Days 3 and 7 and compare to sample measurements at baseline (before commencement of treatment).

Comparisons will be made between the groups using ANCOVA (and post-hoc tests if significant differences are identified) will be used to detect difference in means adjusting for baseline values.

In addition, all analyses will be undertaken by comparison (i.e. Carbocisteine vs No carbocisteine and Hypertonic saline vs No hypertonic saline).

Doc No: ST06-RD01 Page **12** of **29**

[figure not shown]

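### The drug-versus-no-drug ANCOVAs adjust for baseline only, so unequal per-protocol losses let a small part of one drug's effect into the other's estimate

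*SAP*

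**What the plan says.** Section 4 (Definition of terms) gives one per-protocol population: "Per protocol analysis will be undertaken on the population who receive the complete treatment dose". It adds that UACM patients "will be excluded from the per protocol analysis if they commence a non-trial mucoactive". A separate entry sets a compliance threshold: "Patients who receive ≥90% available doses will be considered as compliant". The SAP does not link that threshold to the per-protocol definition, and it splits neither by drug.

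Section 7 makes the set primary: "The primary analysis will be conducted on outcome data from the per-protocol population". It closes with: "In addition, all analyses will be undertaken by comparison (i.e. Carbocisteine vs No carbocisteine and Hypertonic saline vs No hypertonic saline".

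For the between-group tests, sections 7 and 8.5 name an ANCOVA adjusted for baseline values. For the primary outcome, section 8.5 identifies the covariate as the Day 0 solids percentage. No factor for the other drug is mentioned.

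**The concern.** The four arms are UACM, carbocisteine alone, saline alone and both. A carbocisteine-versus-none comparison pools two arms on each side. While the arms are equal in size, half of each side is on saline and any saline effect cancels. Per-protocol selection can break that equality, because patients leave for different reasons in different arms. Once the saline share differs between the two sides, an ANCOVA without a saline term attributes part of the saline effect to carbocisteine. The same holds with the drugs exchanged.

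A single per-protocol set also means, on its natural reading, that a patient who fails on one drug leaves the comparison of the other drug too, which costs some precision.

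**Working it through.** **Inputs from the SAP (section 5).** "A sample size of 85 in each of our treatment groups will have 90% power to detect a difference in means of 1.15" wt%, "assuming that the common standard deviation is 2.3" wt%, two-sided 0.05.

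**The plan's figure.** n per arm = 2(1.960 + 1.282)² × (2.3/1.15)² = 84.1, rounded up to 85. The exact t-test calculation gives 85.03 and power 0.900. The stated 85 reproduces.

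**Assumptions.** The SAP gives no exclusion rates. Let p be the share not completing a drug, q = 1 − p, and u the share of UACM patients excluded. Each arm starts at 85, the two drugs' effects add, and the saline effect is set at 1.15 wt%, the plan's own target difference.

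**Imbalance in the carbocisteine comparison.**

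- Saline share, carbocisteine side = n(both) / [n(carbocisteine) + n(both)].
- Saline share, other side = n(saline) / [n(UACM) + n(saline)].
- Shift in the unadjusted estimate = (difference in shares) × 1.15.

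In the table, concurrent means that combination patients stop both drugs together, and independent means that they stop each drug separately. p is 15%.

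| Stopping, u | UACM / carbocisteine / saline / both | Saline share, carbocisteine side v other | Shift (wt%) |
|---|---|---|---|
| Concurrent, u = 0 | 85 / 72.25 / 72.25 / 72.25 | 50.0% v 45.9% | +0.047 |
| Concurrent, u = 15% | 72.25 in every arm | 50.0% v 50.0% | 0 |
| Concurrent, u = 30% | 59.5 / 72.25 / 72.25 / 72.25 | 50.0% v 54.8% | −0.056 |
| Independent, u = 0 | 85 / 72.25 / 72.25 / 61.4 | 45.9% v 45.9% | 0 |
| Independent, u = 15% | 72.25 / 72.25 / 72.25 / 61.4 | 45.9% v 50.0% | −0.047 |

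The shift vanishes only when n(both)/n(carbocisteine) equals n(saline)/n(UACM). With concurrent stopping and u = 0, the shift is 1.15 × [0.5 − q/(1+q)], which is 0.030, 0.047, 0.064 and 0.082 wt% at p = 10, 15, 20 and 25%.

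**Against the standard error.** In the first row, SE = 2.3 × √(1/144.5 + 1/157.25) = 0.265. If saline has the assumed effect and is left out of the model, the within-side variance rises to 2.3² + 1.15²/4 = 5.29 + 0.33 = 5.62, and the SE is about 0.273. The shift of 0.047 is then about 0.17 of a standard error.

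**Effect of adding the factor.** With balanced shares, the ratio of standard errors is √(5.29/5.62) = 0.970, a cut of about 3%. If saline has no effect, the stratified SE in the first row is 2.3 / √[1/(1/85 + 1/72.25) + 1/(2/72.25)] = 0.265, the same to three decimals. Adding the factor therefore costs essentially nothing.

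**Drug-specific membership as an alternative.** Here only adherence to the compared drug counts, which keeps 170q v 170 patients. SE relative to the single-set reading, with u = 0:

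| p | Independent stopping: 85q + 85q² v 85 + 85q | Concurrent stopping: 170q v 85 + 85q |
|---|---|---|
| 10% | 0.975 | 0.988 |
| 15% | 0.962 | 0.982 |
| 20% | 0.949 | 0.976 |
| 25% | 0.935 | 0.971 |

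The gain is 2.5 to 6.5%, or about 1 to 3% if both drugs stop together. It has a price. Under concurrent stopping at 15%, every retained combination patient has completed saline, but only 72.25 of the 85 retained saline-only patients have. Saline completion is then 50% v 72.25/170 = 42.5%. Adjusting for saline allocation does not remove this. Within the saline stratum the exposure gap is 15%, and with equal stratum weights the bias is 0.5 × 0.15 × 1.15 = 0.086, about 0.09 wt%, if stopping saline forfeits its whole effect.

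**The case against.** The strongest case against acting is size. The by-drug analyses are additional. They pool two arms per side in a study powered for one arm against one, and a shift of about 0.05 wt% would rarely change a conclusion. Every rate behind it is assumed. All of that stands, and it caps the importance of the point. It does not argue against a model term that costs nothing.

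A reader might infer three stronger things.

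- **That the SAP imposes a whole-regimen rule.** It does not say so. Section 4 leaves open how its definition applies in the combination arm and in each by-drug comparison. Removal from both comparisons is the natural reading of a single set, not a stated rule.
- **That the combination arm is thinned most.** This needs stopping that is not fully concurrent, and UACM exclusions that stay below 1 − q² (19% at p = 10%, 36% at p = 20%). UACM has its own exclusion route, at an unknown rate. Many of the termination reasons in the Appendix 1 treatment table, such as ICU discharge, death or the end of active treatment, would stop both drugs at once. One that could apply to a single drug is "Decision from the attending ICU physician that the study drug should be discontinued on safety grounds". With no UACM exclusions, extra thinning needs non-concurrent stopping and the imbalance needs correlated stopping, so the two harms do not peak together.
- **That drug-specific membership is the remedy.** Its gain is modest, and it can separate allocation from actual exposure to the other drug. Nor does it touch selection after randomisation, a weightier and separate matter.

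**Conclusion.** The point holds as a minor one. A single per-protocol set serves both the four-arm and the by-drug analyses, and the by-drug ANCOVA has no term for the other drug. Unequal exclusions can therefore move one drug's estimate by a fraction of the other's effect. The size is about 0.05 wt% for a 1.15 wt% saline effect with 15% concurrent stopping and no UACM exclusions. It is zero under some patterns and of opposite sign under others. The figures rest on assumed rates, 85 patients per arm before exclusions, additive drug effects and the plan's SD of 2.3 wt%. The documents do not support a claim of serious lost power: even at 25% independent stopping, power for 1.15 wt% in the pooled comparison is 97.9% with the single set and 98.9% with drug-specific membership.

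**What to change.** In sections 7 and 8.5, state that every by-drug ANCOVA includes allocation to the other drug as a two-level factor alongside the baseline value. The cost is one sentence and one model term. With additive effects it removes the imbalance, and it slightly improves precision if the other drug works.

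In section 4, state how the per-protocol definition and the 90% threshold apply to each drug in the combination arm and to each by-drug comparison. This is wording only.

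If drug-specific membership is wanted, make it at most a sensitivity analysis, note that its patient set differs from that of the four-arm table, and report saline and carbocisteine completion on each side. It needs dosing records held by drug, which this SAP does not confirm.
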